- Review and collect Memory Aid / Subject Diary, including verification of entries with the subject.
- Record any unsolicited AEs since the last study visit.
- Perform symptom-driven physical examination.
- Laboratory tests:
 - Lyme borreliosis screening test: For serological screening on previous infection with Lyme borreliosis, a commercially available Lyme borreliosis screening test will be performed. Serum samples that are tested positive will be verified by a confirmatory immunoblot.
- Collect immunogenicity blood sample

For remote visits:

- Document any changes to concomitant medication/treatments including vaccination(s) since the previous study visit.
- Review of memory aid/diary: Ask subject to read through memory aid/diary or to mail or email pictures of the memory aid/diary upfront to aid the discussion.
- Perform scripted safety assessment. Record any unsolicited AEs since the last study visit.
- Procedures performed by a mobile nurse professional:
 - o Collect immunogenicity sample

Unscheduled Visits:

An unscheduled visit can be held at any time during the study if deemed necessary by the Investigator (e.g. follow-up on unexpected AEs, SAEs or AESIs) or requested by the DSMB. Unscheduled visits and any assessments performed during the visit (e.g. physical examination, laboratory test) should be documented in the source data and the eCRF. For subjects who perform Visit 10/Month 19 remotely and in circumstances where collection of blood samples by the mobile nurse professional or processing of blood samples for safety labs is not feasible, subjects will be asked to come to the study site for an unscheduled visit within 1 month after the remote visit to provide respective blood sample, as applicable.

Early Termination (before Visit 12):

Subjects who terminate participation or who are withdrawn from the study prematurely undergo the following investigations during an Early Termination Visit, if possible:

- Document any changes to concomitant medication/treatments including vaccination(s) since the previous study visit.
- Perform symptom-driven physical examination.
- If Early Termination visit is before Visit 6 in the Main Study Phase or before Visit 10 in the Booster Phase, inspect vaccination site from previous vaccination for (ongoing) Adverse Events.
- Review and collect unreturned subject diaries or Memory Aids, including verification of entries with the subject. Study physician to re-assess causality for any reported medically attended or severe solicited local and systemic AEs.
- Record any unsolicited AEs since the last study visit.
- Laboratory tests:
 - Lyme borreliosis screening test: For serological screening on infection with Lyme borreliosis, a commercially available Lyme borreliosis screening test is performed. Serum samples that are tested positive are verified by a confirmatory immunoblot.
 - Urine pregnancy test: In women of childbearing potential.

The reason for early termination should be clarified in as much detail as possible. If an AE is the reason for early study termination details on that specific AE(s) should be captured.

If the subject is unwilling to perform an ET Visit or an in-person ET visit is not possible due to circumstances of the ongoing COVID-19 situation, a remote visit (e.g., phone/ video call) should be made as soon as possible after termination to follow-up on concomitant medication including vaccination(s) and AEs ongoing (including persisting injection site reactions, if applicable) and any new AEs since the previous study visit should be documented. The reason for early termination should be clarified in as much detail as possible. If an AE is the reason for early study termination details on that specific AE(s) should be captured. See also section 10.3 of the study protocol.

Note: If subject presents at a regular study visit within the acceptable time window and inform that he/she discontinues the study after this visit, the study visit is not performed as an ET visit, but is performed and documented as a regular study visit including all events that are described for respective study visit. In this case a Lyme borreliosis screening test is performed in addition for serological screening on infection with Lyme borreliosis.

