- (2) Visit should preferably be conducted as an in-person visit. If an in-person is not feasible due to COVID-19, e.g. travel restrictions, local recommendations, circumstances at the study site's location that prohibit an in-person visit, or if the PI believes that the subject's safety and well-being might be jeopardized with an in-person visit at the study site due to COVID-19, the visit should be conducted remotely (e.g., phone/ video call). In case subject visit is performed remotely and the COVID-19 situation allows coming to the site at a later time point, the immunogenicity sample should be taken during an unscheduled visit as early as possible within a maximum time window of 2 months after the remote study visit. For Visit 8, subjects should perform the unscheduled visit for immunogenicity blood within a maximum time window of 1 month after the remote study visit.
- (3) Occurs before screening and prior to any study-related procedures.
- (4) Symptoms noted at Visit 1 (prior to first vaccination) are not considered AEs but are recorded as medical history.
- (5) Physical examination includes, but is not limited to assessment of general appearance and skin, head/ eyes/ ears/ nose/ throat, cardiovascular system, respiratory system, abdominal and gastrointestinal system, musculoskeletal system, neurological system and lymph nodes. If applicable, physical examination as well as ECG performed within the study VLA15-201 is acceptable for study VLA15-202 if within the specified visit window.
- (6) Vital signs (Systolic and diastolic blood pressure, pulse rate while seated and at rest) to be measured prior to vaccination (if applicable) and in addition prior to discharge in case subject reports any complaints.
- (7) To be performed prior to vaccination.
- (8) The results of negative HIV tests that are performed up to 30 days before Visit 0 are acceptable (blood: HIV test 3.5 mL). Positive HIV test obtained by ELISA has to be confirmed by a second method (e.g. Westernblot or PCR).

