- (9) If applicable, HIV test, Lyme borreliosis screening test, serum pregnancy test, clinical chemistry tests, hematology tests, and coagulation tests performed at the study site within the study VLA15-201 is acceptable for study VLA15-202 if within the specified visit window. As such, if test results are available, respective blood samples do not need to be collected again for the present study. Similar, if applicable, a baseline serology sample collected at the study site within the study VLA15-201 is acceptable for study VLA15-202 if within the specified visit window.
- (10) A commercially available Lyme borreliosis screening test will be performed (blood: 4 mL). Serum samples that are tested positive have to be verified by a confirmatory immunoblot. LB test results need to be available before randomization and remain valid for 4 weeks.
- (11) For in-person study visits only.
- (12) A baseline serology sample is taken at the screening visit and might be used for retrospective work-up of suspected AESIs (e.g. analysis of Rheumatoid factor (RF), anti citrullinated protein antibodies (ACPA) etc., as appropriate). (blood: 5.0 mL). If applicable, a baseline serology sample collected at the study site within the study VLA15-201 is acceptable for study VLA15-202 if within the specified visit window.
- (13) In women of childbearing potential. A woman is considered of childbearing potential if fertile, following menarche and until becoming post-menopausal unless permanently sterile. A woman who is considered of non-childbearing potential must be e.g. surgically sterilized for at least 3 months prior to Visit 1 (e.g. by hysterectomy, bilateral

salpingectomy, bilateral oophorectomy, trans cervical sterilization), or postmenopausal for at least one year prior to Visit 1. For serum pregnancy test: tests that were performed in study laboratory within visit window and where results are available at study visit are acceptable.

(14) At vaccination visits, all samples have to be obtained before vaccination. Pregnancy results and urinalysis must be available before vaccination.

(15) Creatinine, sodium, potassium, calcium, aspartate aminotransferase (AST), alanine aminotransferase (ALT), alkaline phosphatase, bilirubin, CRP (blood: 8.5 mL). Test results from this study visit do not need to be available before vaccination. Tests that were performed in study laboratory within visit window and where results are available at study visit are acceptable.

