(16) Hemoglobin, hematocrit, erythrocyte count, white blood count, platelets (EDTA blood: 4 mL). Test results from this study visit do not need to be available before vaccination. Tests that were performed in study laboratory within visit window and where results are available at study visit are acceptable.

(17) Prothrombin time, aPTT, fibrinogen (blood: 4.5 mL). Tests that were performed in study laboratory within visit window and where results are available at study visit are acceptable.

(18) Standard urine dipstick: pH, specific gravity, leucocytes, nitrite, protein, glucose, ketones, urobilinogen, bilirubin, erythrocytes. Tests that were performed in study laboratory within visit window and where results are available at study visit are acceptable.

(19) Blood is collected for immunogenicity testing by ELISA and for supportive functional antibody analysis by serum bactericidal assay or animal protection models.

(20) In case subject visit is performed remotely, if the COVID-19 situation allows, the immunogenicity sample should be taken in an unscheduled visit as early as possible, within a maximum time window of 2 months after the remote study visit.

(21) To be performed by study staff otherwise not involved with study conduct to keep the study observer-blinded (i.e. unblinded study staff).

(22) Study vaccine has to be administered by study staff otherwise not involved with study conduct to keep the study observer-blinded. Subjects should be observed for at least 30 min after vaccination for treatment of any immediate reactions.

(23) In case subject visit is performed remotely ask subject to describe the appearance of the injection site, to understand whether there is any residual local reaction. If yes, document as AE.

(24) Except for Visit 1: Body systems for which the subject reports any symptoms should be evaluated and relevant abnormal findings documented as AEs. At vaccination days the symptom-driven physical exam is to be performed before administration of the vaccination.

(25) If subject has any complaints after vaccination, a second symptom-driven physical examination will be performed by the investigator prior to discharge. Subject will only be discharged if in the opinion of the investigator no further concerns exist.

(26) At Visit 1, the subjects are provided with thermometer and measuring tapes. The subjects assess solicited local and systemic AEs themselves over a period of seven consecutive days after each vaccination.

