- If the subject has any complaints after vaccination, perform a symptom-driven physical examination and record vital signs prior to discharge. Only discharge subject if in the opinion of the investigator no further concerns exist.

Visit 6, Day 208/ Month 7 (+/- 10 days):

This visit should preferably be conducted as in-person visit. If an in-person visit cannot be executed or is unacceptable due to COVID-19, e.g. travel restrictions, local recommendations, circumstances at the study site's location that prohibit an in-person visit, or if the PI believes that the subject's safety and well-being might be jeopardized with an in-person visit at the study site due to COVID-19, the visit should be conducted remotely (e.g., phone/ video call).

For in-person visits:

- Document any changes to concomitant medication/treatments including vaccination(s) since the previous study visit.
- Perform symptom-driven physical examination.
- Inspect vaccination site from third vaccination for (ongoing) Adverse Events.
- Review and collect the Subject Diary, including verification of entries with the subject. Clinician to re-assess severity of reported solicited local and systemic AEs. In addition re-assess causality for any reported medically attended or severe solicited local and systemic AEs.
- Record any unsolicited AEs since the last study visit.
- Distribute and explain Memory Aid to document unsolicited Adverse Events. Instruct subject to immediately inform the site in case the subject experiences any severe symptoms or if subject has any suspicion of having Lyme borreliosis.
- Laboratory tests:
 - Urine pregnancy test: In women of childbearing potential.
 - Clinical Chemistry: Creatinine, sodium, potassium, calcium, aspartate aminotransferase (AST), alanine aminotransferase (ALT), alkaline phosphatase, bilirubin, CRP.
 - Hematology: Hemoglobin, hematocrit, erythrocyte count, white blood count, platelets.
 - Urinalysis (standard urine dipstick): pH, specific gravity, leucocytes, nitrite, protein, glucose, ketones, urobilinogen, bilirubin, erythrocytes.
- Collect immunogenicity blood sample.

For remote visits:

- Document any changes to concomitant medication/treatments including vaccination(s) since the previous study visit.
- Inspection of vaccination site from third vaccination: Ask subject to describe the appearance of the injection site, to understand whether there is any residual local reaction. If yes, document as AE.

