- Instruct subject to immediately inform the site in case subject experiences one of the following:
 - any severe adverse event
 - any symptoms suspicion or diagnosis of Lyme borreliosis, e.g. red or bluish-red patch (≥ 5 cm, indicate location), or joint swelling (indicate which joint).
- Perform scripted safety assessment. Record any unsolicited AEs since the last study visit.

In case the subject visit is performed remotely and the COVID-19 situation allows coming to the site at a later time point, the immunogenicity sample should be taken during an unscheduled visit as early as possible within a maximum time window of 2 months after the V7 remote study visit.

Visit 8, Day 545/ Month 18 (+/- 28 days):

This visit should preferably be conducted as an in-person visit. If an in-person is not feasible due to COVID-19, e.g. travel restrictions, local recommendations, circumstances at the study site's location that prohibit an in-person visit, or if the PI believes that the subject's safety and well-being might be jeopardized with an in-person visit at the study site due to COVID-19, the visit should be conducted remotely (e.g., phone/ video call).

For in-person visits:

- Document any changes to concomitant medication/treatments including vaccination(s) since the previous study visit.
- Perform symptom-driven physical examination.
- Review and collect Memory Aid, including verification of entries with the subject.
- Record any unsolicited AEs since the last study visit.
- Laboratory tests:
 - Lyme borreliosis screening test: For serological screening on infection with Lyme borreliosis, a commercially available Lyme borreliosis screening test will be performed. Serum samples that are tested positive will be verified by a confirmatory immunoblot.
 - Urine pregnancy test: In women of childbearing potential.
 - Clinical Chemistry: Creatinine, sodium, potassium, calcium, aspartate aminotransferase (AST), alanine aminotransferase (ALT), alkaline phosphatase, bilirubin, CRP.
 - Hematology: Hemoglobin, hematocrit, erythrocyte count, white blood count, platelets.
 - Urinalysis (standard urine dipstick): pH, specific gravity, leucocytes, nitrite, protein, glucose, ketones, urobilinogen, bilirubin, erythrocytes.
- Collect immunogenicity blood sample.

For remote visits

- Document any changes to concomitant medication/treatments including vaccination(s) since the previous study visit.

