- Review of Memory Aid: Ask subject to read through memory aid/ AE sections of subject diary if previous visits were conducted as remote study visits, or to mail or email pictures of the memory/diary entries upfront to aid the discussion.
- Perform scripted safety assessment. Record any unsolicited AEs since the last study visit.
- Inform subjects of the possibility of an unscheduled visit within 1 month after the remote visit for immunogenicity sample collection, if the COVID19 situation allows.
- If the COVID-19 situation allows coming to the site for an unscheduled visit within 1 month after the remote visit: take immunogenicity sample.

The following procedures are performed for subjects enrolled in the Booster Phase:

Visit 9, Month 18 (Date of Visit 8 (+ 2 max. months)):

Visit 8 and Visit 9 should be combined in one visit if possible; otherwise the time between Visit 8 and Visit 9 should be kept as short as possible (preferably maximum of one month apart). If the COVID19 pandemic mandates, the subject has the possibility to perform the study visit within 2 months after Visit 8. If both visits are scheduled on the same day, all procedures from Visit 8 have to be performed prior to performing procedures from Visit 9.

Signed and dated informed consent for the Booster Phase must be obtained before any study specific procedures are undertaken.

- Check of inclusion and exclusion criteria.
- Check vaccination delay criteria.
- Document any changes to concomitant medication/treatments including vaccination(s) since the Visit 8.
- Perform symptom-driven physical examination, measure vital signs (systolic and diastolic blood pressure, pulse rate) in seated position and at rest, measure oral body temperature (vaccination should be postponed in case of an acute febrile illness).
- Laboratory tests (samples to be taken prior to vaccination):
 - Lyme borreliosis screening test (only to be performed if Visit 9 is later than 1 month after Visit 8): For serological screening on previous infection with Lyme borreliosis, a commercially available Lyme borreliosis screening test will be performed. Serum samples that are tested positive will be verified by a confirmatory immunoblot.
 - Urine pregnancy test: In women of childbearing potential.
 - Urinalysis (standard urine dipstick): pH, specific gravity, leucocytes, nitrite, protein, glucose, ketones, urobilinogen, bilirubin, erythrocytes.

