7. ASSESSMENT OF IMMUNOGENICITY

7.1 Immunogenicity Measurements

Immunogenicity assessments measuring OspA serotype specific by IgG ELISA are performed on samples collected at Visits 1-12, or at respective unscheduled visits after Visit 7 or 8, if one or more of these visits are performed remotely (e.g., phone/ video calls).

[figure not shown]
All steps of the assays are performed at Valneva Austria GmbH Vienna, Department of Clinical Serology according to Standard Operating Procedures (SOPs). The work is performed in an environment that is certified to Biological Safety Level 2 (BSL2), internally audited, and conform to GCLP requirements. Raw data is stored on a separate, secure server in a defined Information Technology environment complying with regulatory standards. Raw data print outs are stored in respective study binders.

Details on the analysis of immunogenicity assessments described below will be provided in the Statistical Analysis Plan (SAP).

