9.7 Data Analyses

Two interim analyses on safety and immunogenicity data will be performed during the Main Study Phase. The first interim analysis was performed once all subjects have completed Visit 6 (i.e. Day 208/Month 7, four weeks after the last primary vaccination) covering safety and immunogenicity data up to Visit 6 including the primary endpoint analysis. The second interim analysis will be performed once all subjects have completed Visit 7 (i.e. Day 365, six months after the last vaccination), covering in addition all safety data collected up to this time point. Final analysis of safety and immunogenicity data from the Main Study Phase will be performed once all subjects have completed the follow-up period up to Visit 8 (i.e. Day 545/Month 18, 12 months after the last vaccination).

In the Booster Phase three data analyses will be performed: A first analysis will be conducted after all subjects completed Visit 10 (Month 19). The second analysis will be performed once all subjects have completed Visit 11 (Month 24). A final analysis on safety and immunogenicity will be performed after the last subject has completed the last study visit at Month 30 (Visit 12) and will include all safety and immunogenicity data up to Month 30.

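### Does the mismatch between the two stated Visit 6 windows put the primary Day 208 result in doubt?

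*Protocol*

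**What the plan says.** The Table of Events for the Main Study Phase (Table 3) prints the Visit 6 window as +4/-10 days in both of its headers. Section 4.2.3 heads the visit "Visit 6, Day 208/ Month 7 (+/- 10 days".

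On blood draws when a visit is held remotely:

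- Table 3 footnote (2) is marked on the visit type of Visits 6, 7 and 8 and Early Termination. It provides for the immunogenicity sample at an unscheduled visit "within a maximum time window of 2 months after the remote study visit", with a shorter limit of 1 month for Visit 8.
- The Visit 6 sample cell carries footnote (11) only: "For in-person study visits only".
- Footnote (20), marked on the Visit 7 and Visit 8 samples, says "the immunogenicity sample should be taken in an unscheduled visit as early as possible".
- Section 4.2.3 writes a later draw into remote Visit 7, "within a maximum time window of 2 months after the V7 remote study visit", and into remote Visit 8, "within 1 month after the remote visit for immunogenicity sample collection". The remote Visit 6 list has none.
- Section 7.1 covers samples from the regular visits "or at respective unscheduled visits after Visit 7 or 8".

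Section 9.7 states: "The first interim analysis was performed once all subjects have completed Visit 6". That analysis included the primary endpoint.

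**The concern.** Day 208 is the only primary time point. It is also the reference for the booster fold rises at Months 19, 24 and 30. Of the post-baseline Main Study visits, Visit 6 alone has two different windows; Visits 2 to 5, 7 and 8 agree between Table 3 and Section 4.2.3. A reader could fear that the set of samples counted as Day 208 is undefined, first for ordinary visits on Days 213 to 218, and second for draws made weeks after a remote visit. If titers fall after their peak, late samples would lower the Day 208 geometric mean titers and raise the later fold rises measured against them.

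**Working it through.** **The two windows**

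| Source | Lower limit | Upper limit | Calendar days |
|---|---|---|---|
| Table 3 (+4/-10) | 208 - 10 = 198 | 208 + 4 = 212 | 15 |
| Section 4.2.3 (+/-10) | 208 - 10 = 198 | 208 + 10 = 218 | 21 |

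The lower limits agree. The disputed days are 213 to 218: 6 days, or 6/21 = 29% of the wider window. That is a share of calendar days, not of samples.

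**Time since the third dose**

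For a dose exactly on Day 180, the disputed days lie 213 - 180 = 33 to 218 - 180 = 38 days after it, against a nominal 208 - 180 = 28. Visit 5 has its own window of +/-7 days (Days 173 to 187). If Visit 6 is counted from Day 1 (an assumption; the protocol does not say):

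- Disputed days: from 213 - 187 = 26 to 218 - 173 = 45 days after dose 3.
- Narrower Table 3 window: up to 212 - 173 = 39 days after dose 3.

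Some samples in the disputed span are thus closer to the nominal interval than some that both passages accept.

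**The later draw after a remote Visit 6**

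Footnote (2) is marked on Visit 6 and shortens the limit for Visit 8 alone, so its 2-month limit naturally covers Visits 6 and 7. Footnote (11) does not bar this: it rules out a draw at a remote visit, and an unscheduled site visit is in person. The remote Visit 6 list is silent. Only Section 7.1 and the placement of footnote (20) point the other way, and they do so by omission.

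Taking 2 months as 60 to 62 days (assumption), the latest such draw falls on Day 212 + 60 = 272 to 218 + 62 = 280. That is 92 to 100 days after a Day 180 dose. How many such samples exist, if any, is not stated.

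**What depends on the window**

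- *Per-protocol set.* Section 9.2 excludes subjects for fewer than three vaccinations, wrong study medication, or exclusion criteria 2, 8, 9 or 14. No criterion uses the Visit 6 window. Further criteria may be set in the SAP, and final decisions are made case by case at a data review meeting.
- *Sample size.* Section 9.6 uses GMTs of 61.3 and 100.4 and a log10 SD of 0.51. With delta = log10(100.4/61.3) = 0.2143, n = 2(1.960 + 0.842)^2 x 0.51^2 / 0.2143^2, which rounds up to 89 per group. This is in line with the stated 90, and no sampling window enters it.
- *Timing.* The version is dated 02-Nov-2021. Section 1.4.3.2 already reports Day 208 titers, and Section 4.2.2 says the 180 µg dose was selected on the Day 208 interim.

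**The case for a change.** The strongest case for acting is that an SAP can set an analysis window but cannot make two protocol passages agree, and that one use of Day 208 values was still ahead. The Booster Phase began in January 2021 and Visit 12 falls 12 months (+/-28 days) after Visit 9. The Month 30 visits could therefore not start before about December 2021, after this version. A sensitivity analysis limited to one window, or adjusted for actual days since dose 3, would cost little because the dates are on file.

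The first point stands: the passages disagree and ought to be aligned. The second does not carry through to a change in the analysis. The Day 208 sample came before booster randomisation, so its timing cannot depend on the booster arm. In the Main Study Phase, site staff stayed blinded until shortly before Visit 8 (Section 4.2.10), so there is no evident route by which late sampling would favour one dose group. A restriction by study day could also drop a sample at 26 days after dose 3 and keep one at 39. An analysis added after unblinding, with no sign that any sample is affected, would not sharpen a conclusion. Which samples are treated as Day 208 values is a question that Sections 7.1, 9.1 and 9.2 send to the SAP and data review.

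**Conclusion.** This is a clerical mismatch at a completed visit, and no change to the plan follows. The two windows differ by six days at the upper limit. Footnote (2) supplies the draw after a remote Visit 6 that the other passages leave out. Aligning Table 3, Section 4.2.3 and Section 7.1 would be good housekeeping, but it alters no blood draw, analysis set or conclusion. The document alone cannot show which window was intended.

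This rests on three things: the Day 208 analysis was done before this version, as Section 9.7 states; no per-protocol criterion in Section 9.2 uses the window; and the SAP, which is not at hand, or the data review meeting settles the handling of late samples, as the protocol says. The size of any shift in the titers cannot be calculated from the document. Bias between randomised groups is likely small.
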